2.2. Protocol Violations

Participants are not required to follow special instructions specific to the Investigational Product (IP) used in this clinical trial. Participants will be provided with Investigator emergency contact information and advised to report all AEs. While every effort should be made to avoid protocol deviations, should an important deviation be discovered, the Sponsor must be informed immediately. Any protocol deviation impacting participant safety must be reported to the Medical Monitor immediately.

At the discretion of the Sponsor, major protocol violations, as determined by a review of the data prior to unblinding of the study results and the conduct of statistical analyses, may result in the remove of a participant's data from the PP population. The Sponsor or designee will be responsible for producing the final protocol violation file (formatted as a Microsoft Excel file), in collaboration with Veristat and the data monitoring group as applicable; this file will include a description of the protocol violation and clearly identify whether or not this violation warrants exclusion from the PP population. This file will be finalized prior to hard database lock.

All protocol violations will be presented in a data listing.

3. GENERAL STATISTICAL METHODS

3.1. Sample Size Justification

The study is to be conducted in two parts. No formal power analysis is applicable to Part 1 of this trial, as descriptive statistics will be used to summarize the data.

For Part 1 of the trial with 32 INO-4700 administered participants per study group, the study provides 95% confidence that the true incidence of serious adverse events (SAEs) is <11% if no SAEs are observed in a study group. For all the study groups combined in Part 1 of the trial with 160 INO-4700 administered participants, the study provides 95% confidence that the true incidence of SAEs is <3% if no SAEs are observed in this study phase. For all study groups combined across Parts 1 and 2 of the trial with 460 INO-4700 administered participants, the study provides 95% confidence that the true incidence of SAEs is <1% if no SAEs are observed.

For Part 2 of this trial, an evaluable sample of 260 active participants treated with INO-4700, which will be used for formal hypothesis testing, provides >90% power to detect an INO-4700 overall immunological response rate of 70% or higher should this overall response rate truly be 80%, using a one-sided type 1 error rate of 0.025.

3.2. General Methods

All data listings that contain an evaluation date will have a relative study day (Rel Day). Pre-treatment and on-treatment study days are numbered relative to the day of the first dose of study medication (Day 0) which is designated as Rel Day 1. The preceding day is Rel Day -1, the day before that is Rel Day -2, etc. There is no Rel Day 0.

All output will be incorporated into Microsoft Word or Excel files, or Adobe Acrobat PDF files, sorted and labeled according to the International Council on Harmonisation (ICH) recommendations, and formatted to the appropriate page size(s).

Tabulations will be produced for appropriate demographic, baseline, immunogenicity, and safety parameters. For categorical variables, summary tabulations of the number and percentage of participants within each category of the parameter will be presented. For continuous variables, the number of participants, mean, median, standard deviation (SD), minimum, and maximum values will be presented. Summarizations will be presented by study group and overall as applicable for Part 1, and by treatment groups (randomized to active, randomized to placebo, randomized to an active booster with previous active dose, to placebo booster dose who had previously 2 active doses, and the number randomized to three placebo doses) and overall as applicable for Part 2. All data from active vs. placebo treatments will be pooled and summarized.

Formal statistical hypothesis testing will be performed on the primary immunogenicity endpoint (see [Section 1.2.5.1.](#)) with all tests conducted at the 1-sided, 0.025 level of significance. Summary statistics will be presented, as well as confidence intervals (CIs) on selected parameters, as described in the sections below.

3.3. Computing Environment

All statistical analyses will be performed using SAS statistical software Version 9.4. Adverse events will be coded using the current Medical Dictionary for Regulatory Activities (MedDRA) Version 22.1 or higher.

All output will be incorporated into Microsoft Word or Excel files, or Adobe Acrobat PDF files, sorted and labeled according to the ICH recommendations, and formatted to the appropriate page sizes.

3.4. Baseline Definitions

For all analyses, baseline will be defined as the most recent measurement prior to the first administration of study drug.

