- Collect urine for routine urinalysis ([Section 6.4](#));
- Collect whole blood and serum for immunology assessment ([Section 6.4.6](#)).

6.1.2.7 Week 12

Part 1

The following evaluations will be collected during the follow-up phone call visit:

- Collect all present and/or new or ongoing adverse events.

Part 2 if Day 0/Week 4 Dosing Regimen is Optimal

The following evaluations will be performed at this visit:

- Collect all present and/or new or ongoing adverse events;
- Document any present conditions and concomitant illnesses;
- Collect whole blood and serum for immunology assessment ([Section 6.4.6](#)).

Part 2 if Day 0/Week 8 Dosing Regimen is Optimal

The following evaluations will be collected during the follow-up phone call visit:

- Collect all present and/or new or ongoing adverse events.

6.1.2.8 Week 30

The following evaluations will be collected during the follow-up phone call visit:

- Collect all present and/or new or ongoing adverse events.

6.1.2.9 Week 48

Part 1

The following evaluations will be performed at this visit (End of Study visit):

- Collect all present and/or new or ongoing adverse events;
- Document any present conditions and concomitant illnesses;
- Record current concomitant medications/treatments ([Section 6.4.7](#));
- Full physical examination ([Section 6.4](#));
- Record vital signs ([Section 6.4](#));
- Collect blood for CBC with differential, serum chemistry and liver function ([Section 6.4](#));
- Collect urine for routine urinalysis ([Section 6.4](#));
- Collect whole blood and serum for immunology assessment ([Section 6.4.6](#)).

Part 2

The Week 48 visit will be the End of Study visit for participants receiving only two doses. The Week 48 visit will be the last dosing visit for participants receiving three doses. The

following evaluations will be performed on **Week 48 (complete prior to IP administration for Part 2 participants receiving a third/booster dose)**:

- Collect all present and/or new or ongoing adverse events;
- Document any present conditions and concomitant illnesses;
- Record current concomitant medications/treatments ([Section 6.4.7](#));
- Targeted physical examination ([Section 6.4](#)) for Part 2 participants receiving a third/booster dose;
- Full physical examination ([Section 6.4](#)) for Part 2 participants receiving two doses only;
- Record vital signs ([Section 6.4](#));
- Collect blood for CBC with differential, serum chemistry and liver function ([Section 6.4](#));

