6.4.6 PERIPHERAL BLOOD IMMUNOGENICITY ASSESSMENTS

Whole blood and serum samples will be obtained to assess overall immune response. Immunology blood and serum samples are to be collected at Screening and select visits during the study. Both Screening and Day 0 immunology samples are required to enable all immunology testing. However, at the Principal Investigator’s discretion, collection of the screening immunology samples may be postponed and collected along with the Day 0 samples. Details of the immunology sample collection and shipment information will be provided in the Laboratory Manual. The T and B cell immune responses to INO-4700 will be measured using assays that include but are not limited to ELISA, neutralization, assessment of immunological gene expression, assessment of immunological protein expression, flow cytometry and ELISPOT.

An immune responder is defined as having either an increase in vaccine antibody titer compared to baseline or an increase in the number of vaccine specific IFN-gamma secreting cells as compared to baseline.

Determination of analysis of collected samples for immunological endpoints will be determined on an ongoing basis throughout the study.

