8.2 GENERAL CONSIDERATIONS

The statistical analysis of the data will be performed by Inovio Pharmaceuticals, or its representative. This is a randomized across Study Group, investigator-and-participant blinded, placebo-controlled (SSC-0001), multi-center phase 2a trial to evaluate the safety, tolerability and immunological profile of INO-4700 administered in healthy adult volunteers. Approximately 542 volunteers will be evaluated across two (2) parts: Part 1 Dose Finding and Part 2 Expansion.

Approximately 192 participants in Part 1 will be randomized across each group (A through I; see [Table 1](#)) to receive either INO-4700 or placebo. Upon completion of the Week 10 visit by all Part 1 participants including evaluable immunological data from all Study Groups, one optimal Study Group dose and regimen will be selected for expansion into Part 2. Participants in Part 1 will be followed until Week 48.

Approximately 350 participants in Part 2 will be randomized to receive the optimal dose of INO-4700 or placebo (see [Table 2](#)). The first 225 participants randomized in parallel to three Study Groups will receive a third dose of either INO-4700 or placebo at Week 48. Participants will either receive a week 48 active treatment administration on top of their two prior active treatment administrations (N=100), or a week 48 placebo administration on top of their two prior active treatment administrations (N=100) or a week 48 placebo administration on top of two prior placebo administrations (N=25). Collectively, these first 225 participants will be followed until Week 68. The remaining 125 participants will be randomized in parallel to either 2 active treatment administrations (N=100) or 2 placebo administrations (N=25) and followed until Week 48.

Details on the Study Group design and conduct and frequency of DMSB meetings can be found in [Sections 3.0](#) and [12.1](#).

The trial's primary analyses pertains to the evaluation of the tolerability, safety and overall immune response to INO-4700 administered by ID injection followed by EP in healthy volunteers. Exploratory analyses concern the evaluation of the expanded immunological response to INO-4700 delivered by ID injection followed by EP, the cellular (T cell) and humoral immune response to boosting with a third INO-4700 ID injection followed by EP and the evaluation of the cross reactivity of other coronavirus spike proteins to the humoral

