8.5.9 EXPLORATORY ANALYSES

T and B post baseline cell number will be analyzed descriptively by Study Group using the mean or median and associated 95% confidence intervals.

In Part 2, treatment difference comparisons will include a comparison of two dose INO-4700 participants who are boosted with INO-4700 versus two dose INO-4700 participants who are boosted with placebo.

Exploratory ANCOVA and Logistic models may be fit that include baseline, confounder variables such as age, antibodies to other coronaviruses and gender to test the relationship between study group and different immune response variables. The relationship between antibodies to other coronaviruses and humoral immune responses will be explored using regression methods such as linear regression.

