In Part 2B, a booster dose will be administered to a subset of the participants from Part 2A. The first 200 participants from the Active treatment group will be randomized to receive either a booster dose or placebo at Week 48 (in addition to the first 2 doses at Day 0 and Week 4 or 8). Similarly, the first 25 participants from the Part 2A Placebo group will receive placebo at Week 48 as a control for Part 2B. All participants receiving a third dose at Week 48 (collectively 225 participants) will be followed for 68 weeks from the Day 0 dosing (i.e., Week 68 will be the planned End of Study [EOS] visit). These 225 patients will be enrolled first. The remaining 125 participants in Part 2A (i.e., those receiving only 2 doses) will be followed for 48 weeks from the Day 0 dosing (i.e., Week 48 will be the planned EOS visit).

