1.2.5.3. Exploratory Parameters

The exploratory endpoint of expanded immune response parameters will include (provided there are available samples):

- Change in T and B cell immunologic proteins levels
- Change in levels of mRNA for genes of interest
- Antibodies to other coronaviruses

In addition to the overall immune response, endpoints to determine the response to the booster dose response for selected participants will be measured, including

- MERS-CoV antigen specific antibodies
- Antigen-specific cytokine-producing T cell responses
- T and B cell responses from immunogenicity assays

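### The pre-booster Week 48 sample has no planned role in the Part 2B booster analysis, because one pre-first-dose baseline serves every analysis

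*SAP*

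**What the plan says.** SAP 3.4 sets a single reference value: "For all analyses, baseline will be defined as the most recent measurement prior to the first administration of study drug". Neither document defines a separate baseline for the third dose.

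Protocol 6.4.6 builds responder status on that reference: "An immune responder is defined as having either an increase in vaccine antibody titer compared to baseline", or a rise over baseline in IFN-gamma secreting cells. SAP 4.3.1 summarizes cellular response increases by group. Binding antibody titers are summarized as geometric means by group, which need no baseline.

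For the booster, SAP 1.2.5.3 says that "endpoints to determine the response to the booster dose response for selected participants will be measured". Protocol 8.5.9 names the contrast as "two dose INO-4700 participants who are boosted with INO-4700 versus two dose INO-4700 participants who are boosted with placebo", but gives no endpoint, visit, model or reference value for it. SAP 4.3.1 contains no booster-specific analysis. SAP 3.6 allows optional ANCOVA and logistic models whose covariates may include baseline values and unspecified others.

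SAP 1.2.1 makes the contrast a randomized one: "The first 200 participants from the Active treatment group will be randomized to receive either a booster dose or placebo at Week 48". Protocol 8.2 gives 100 participants per arm. In Protocol 6.1.2.9 (Week 48), whole blood and serum for immunology are on the list marked "complete prior to IP administration for Part 2 participants receiving a third/booster dose". Post-booster immunology samples follow at Weeks 50 and 68 (Protocol 3.6).

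**The concern.** The third exposure has its own natural reference, the value just before it, and the protocol already collects it. The SAP's universal baseline passes over it in favour of a value about a year older. Three consequences follow.

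- A participant still above Day 0 because of doses 1 and 2 counts as a responder at Week 50 even after a placebo third dose.
- A within-arm rise from Day 0 cannot be read as the effect of the booster.
- The between-arm titer comparison carries all the person-to-person variation in response that already existed at Week 48, although that variation has been measured and could be removed.

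At stake is how well Part 2B could answer its exploratory question about a third dose.

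**Working it through.** **The plan's own figure.** Neither document gives power or precision for the booster comparison. The only power statement (Protocol 8.6, SAP 3.1) concerns the Part 2 one-sample test: 260 evaluable, 70% versus 80%, one-sided 0.025, power above 90%. It reproduces. The smallest rejecting count is 197 of 260, the exact size is 0.0232 and the exact power is 96.0%. It has no bearing on the booster contrast.

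**Inputs for the booster contrast.** There are 100 per arm (Protocol 8.2). Two-sided 0.05 is assumed. The documents give no SD and no correlation rho between the Week 48 and post-booster values. Results are therefore in SD units over a range of rho, with equal SD at the two visits.

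**Is the between-arm contrast biased?** The two arms receive the same treatment until the third dose, so the mean residual response R is common to both. The boosted arm has mean R + d, the placebo-boosted arm has mean R, and the difference is d. A simulation confirmed this with 4,000 replicates, true d = 0.40 SD, assumed R = 2.0 SD, and Day 0 SD 0.4 with correlation 0.1 to later values. At rho 0.7:

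| Analysis | Mean estimate | SE |
|---|---|---|
| Post-booster value only | 0.40 | 0.138 |
| Change from Day 0 | 0.40 | 0.145 |
| ANCOVA on Day 0 | 0.40 | 0.138 |
| Change from Week 48 | 0.40 | 0.109 |
| ANCOVA on Week 48 | 0.40 | 0.100 |

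Every choice recovers the true effect; only precision differs. Within the boosted arm, by contrast, the mean change is 2.40 SD from Day 0 (R + d = 2.0 + 0.4) and 0.40 SD from Week 48.

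**Precision.** The unadjusted SE is sqrt(2/100) = 0.141 SD. ANCOVA on Week 48 multiplies it by sqrt(1 − rho²), and the equivalent sample size is 100/(1 − rho²) per arm. A plain change score has variance 2(1 − rho) relative to the unadjusted value.

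| rho | CI width vs unadjusted | Equivalent n per arm | Power for 0.4 SD, ANCOVA | Power for 0.4 SD, change score |
|---|---|---|---|---|
| 0.3 | 95% | 110 | 84.3% | 66.7% |
| 0.5 | 87% | 133 | 90.4% | 80.7% |
| 0.7 | 71% | 196 | 97.7% | 95.5% |
| 0.8 | 60% | 278 | 99.7% | 99.4% |

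Unadjusted power for 0.4 SD is 80.7%. The change score beats the unadjusted comparison only when 2(1 − rho) < 1, that is rho > 0.5, and is below ANCOVA throughout the table.

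**Responder rate against Day 0.** If a share r of the placebo-boosted arm still responds, and boosted participants who would have responded anyway remain responders, the boosted rate is r + (1 − r)c, where c is the share of the rest that converts. The difference is (1 − r)c, at most 1 − r. With c = 0.5 (assumed) and 100 per arm, using the normal approximation:

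| r | Boosted rate | Largest possible difference | Power |
|---|---|---|---|
| 0.50 | 0.75 | 0.50 | 96% |
| 0.70 | 0.85 | 0.30 | 72% |
| 0.80 | 0.90 | 0.20 | 51% |
| 0.92 | 0.96 | 0.08 | 22% |

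**The case against.** The strongest reply is that the contrast is between randomized arms, so residual response cancels and nothing is biased. That stands. A reader might infer that the booster comparison mostly measures what is left of doses 1 and 2. The documents do not support this for the between-arm titer contrast; it is true only of within-arm change from Day 0.

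Second, geometric mean titers use no baseline, and SAP 3.6 leaves room for other covariates. This also stands: adjustment for Week 48 is permitted. It is not planned, however, and the word baseline in SAP 3.6 carries the SAP 3.4 meaning.

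Third, a reader might infer that responder rates would sit near their ceiling in both arms. The documents do not show that. The 92% and 96% in Protocol 1.3.1 were observed after the second immunization in another study, not some 40 weeks later. The same section cites waning antibody after infection as part of the reason for boosting. The later memo also reports that no Part 1 group met the dose-selection criteria, which include a 70% minimum overall response. The ceiling is conditional on an unknown r.

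Fourth, the gain depends on an unknown rho and is slight at 0.3. This stands, which is why the range is shown.

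Finally, the Day 0 reference validly describes total response after three doses versus two. A Week 48 reference complements it and need not replace it.

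**Conclusion.** The concern holds as a gap in prespecification. One pre-first-dose baseline governs all analyses, and the pre-booster Week 48 value has no planned use as reference or covariate. The randomized titer contrast is unbiased but less precise than the data allow. The interval could be 5% narrower at rho 0.3 and 40% narrower at rho 0.8. Within-arm change from Day 0 cannot isolate the booster effect, and the Day 0 responder difference is capped at 1 − r. Rho, r and the conversion share are assumptions; the documents supply none of them.

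The point is minor. Boosting is an exploratory objective with no power claim, and a later protocol administrative memo states that the trial will not proceed to Part 2. No Part 2B result is affected, but the written Part 2B plan still has the gap. A reader might extend the argument to laboratory and vital-sign changes after the third dose; nothing in the documents makes that case, and it is not part of this point.

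**What to change.** In SAP 3.4, add that the reference value for the Part 2B booster immunology analysis is the Week 48 pre-dose value, keeping the existing baseline elsewhere. In SAP 3.6, prespecify ANCOVA for Active-Booster versus Active-Placebo on log titer and on transformed ELISPOT values at Weeks 50 and 68, with the Week 48 value as covariate. Do not use a plain change score, which loses precision if rho is below 0.5.

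The Week 48 value is a legitimate covariate even if allocation was fixed at entry, because it is taken before the two arms are treated differently.

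Report any booster-response rate relative to Week 48 alongside the Day 0 responder rate, with its threshold stated in advance so that assay noise alone does not create responders.

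The cost is a few sentences in the SAP and one covariate. The samples are already scheduled.

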3.5. Methods of Pooling Data

Data will be pooled across study sites.

3.6. Adjustments for Covariates

Exploratory Analysis of Covariance (ANCOVA) and logistic regression models may be fitted to study the relationship between study group and different immune response variables. Possible covariates may include baseline values, age, antibodies, gender, and other covariates to test the relationship between study group and different immune response variables. The relationship between antibodies to other coronaviruses and humoral immune responses will be explored using regression methods such as linear regression.

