4.3. Immunology, Safety, and Exploratory Evaluations

4.3.1. Immunology Evaluations

The following immunogenicity analyses will be conducted on participants in the PP and mITT study populations.

In Part 1, the difference in percentage of overall immune responders including seroconverters (i.e. positive titer) between all pairs of INO-4700 study groups will be calculated along with corresponding exact (Clopper-Pearson) 95% CIs. The T and B cell immune responses to INO-4700 will be measured using assays that include ELISA, neutralization, assessment of immunological gene expression, assessment of immunological protein expression, flow cytometry, and ELISPOT.

In Part 2, the primary hypothesis of $H_0: p \leq 70\%$ versus $H_1: p > 70\%$ will be tested with an exact test of a binomial proportion. In addition, the binding antibody titer difference between INO-4700 and placebo will be analyzed using the geometric mean fold ratio and associated 95% confidence interval. Percent neutralizing antibodies and antigen specific cellular immune response differences between INO-4700 and placebo will be analyzed using the difference in medians and associated 95% CIs.

For both Part 1 and Part 2, antigen specific binding antibody titers, MERS-CoV neutralizing antibody titers, antibodies to other coronaviruses, and specific cellular immune responses will

be analyzed by study group and treatment group, respectively. Time to peak post-baseline titers will be summarized using descriptive statistics. Binding antibody titer will be analyzed for each study group using the geometric mean and associated 95% CIs. Percent neutralizing antibodies and antigen specific cellular immune response increases will be analyzed for each study group using medians, inter-quartile range and 95% CIs. Percentage with overall immune response, inclusive of seroconversion and corresponding 95% Clopper-Pearson CIs will be analyzed within each study and treatment group.

All immunologic data will be presented in data listings.

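### Free improvement in precision: SAP 4.3.1 leaves the INO-4700 vs placebo titer ratio undefined and without a covariate, though baseline titers are collected and could be a pre-specified adjustment

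*SAP*

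**What the plan says.** For Part 2, SAP 4.3.1 states that "the binding antibody titer difference between INO-4700 and placebo will be analyzed using the geometric mean fold ratio and associated 95% confidence interval". Neutralizing and cellular responses are compared by medians: "cellular immune response differences between INO-4700 and placebo will be analyzed using the difference in medians and associated 95% CIs". Protocol 8.5.2 has the same plan. Neither document names a covariate for these contrasts, and neither defines the fold ratio.

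Covariates between groups appear only as an option. SAP 3.6 says that exploratory ANCOVA and "logistic regression models may be fitted to study the relationship between study group and different immune response variables", and adds: "Possible covariates may include baseline values, age, antibodies, gender, and other covariates". Protocol 8.5.9 likewise allows exploratory models with baseline and "confounder variables such as age, antibodies to other coronaviruses and gender". One separate analysis is firm: "The relationship between antibodies to other coronaviruses and humoral immune responses will be explored using regression methods such as linear regression".

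The baseline data are planned for. Protocol 6.4.6 requires both screening and Day 0 immunology samples (both may be drawn on Day 0), and SAP 3.4 defines baseline as the last value before first dose.

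The formal test is a different analysis. It is an exact binomial test of the response rate in the active arm against 70% (SAP 4.3.1), with power above 90% for 260 evaluable participants (SAP 3.1).

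**The concern.** Two things are left loose.

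The estimator is ambiguous. A geometric mean fold ratio can mean the ratio of post-dose geometric means, which ignores baseline, or the ratio of geometric mean fold-rises, which is a change-score analysis. These have different standard errors, and two analysts could program different things from the same sentence.

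The natural use of baseline, as a covariate, is optional and its covariate list is open. A sponsor-level review of unblinded group summaries is planned at Part 2 Week 12, so a model not fixed before then could be chosen with group results in view.

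At stake is the width of the intervals on the active-placebo titer ratio and a single agreed definition of that ratio. The placebo arm is small (50 against 300 planned), so it dominates the standard error. That is where free precision helps most.

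**Working it through.** **1. The plan's own figure.** Inputs from SAP 3.1: n = 260 active, null 70%, alternative 80%, one-sided 0.025. The smallest rejection count is 197 responders (75.8%). Exact type 1 error is 0.0232 and exact power is 96.0%, consistent with the stated figure of more than 90%. This is a one-sample test, so baseline adjustment of an active-placebo contrast does not alter it. The documents state no power or precision for that contrast.

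**2. Inputs for the contrast.** Planned allocation is 300:50, or 6:1 (SAP 1.2.1). Applying the plan's 260/300 evaluable fraction to placebo gives 50 × 260/300 = 43; this is an assumption. The log10 SD (0.5) and the baseline-outcome correlation ρ are also assumptions.

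**3. Common correlation, equal SDs.** Unadjusted variance is SD² × (1/260 + 1/43). ANCOVA multiplies it by 1 − ρ².

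- SE unadjusted = 0.5 × √(1/260 + 1/43) = 0.0823
- 95% CI factor = 10^(1.96 × 0.0823) = 1.45

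| ρ | 1 − ρ² | Variance reduction | CI factor |
|---|---|---|---|
| 0 | 1.00 | none | 1.45 |
| 0.1 | 0.99 | 1% | 1.45 |
| 0.3 | 0.91 | 9% | 1.43 |
| 0.5 | 0.75 | 25% | 1.38 |

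At the full 300:50, a difference with 80% power unadjusted would have 84% power at ρ = 0.3 and 90% at ρ = 0.5.

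**4. If the fold ratio means fold-rises.** With equal SDs and common ρ, the change-score variance factor is 2(1 − ρ), against 1 − ρ² for ANCOVA. At ρ = 0.2 this is 1.6 against 0.96 (67% larger). At ρ = 0.5 it is 1.0 against 0.75.

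**5. Unequal slopes.** At 6:1 a single pooled slope follows the active arm, while placebo carries (1/43)/(1/43 + 1/260) = 86% of the unadjusted variance under equal SDs. Two illustrations follow, with all parameters assumed. For the baseline-by-arm model the variance is the residual variance in each arm plus (slope difference)² × baseline variance / 303.

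*Case A: equal SDs of 1; ρ = 0.2 active, 0.8 placebo.*

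- Unadjusted: 1/260 + 1/43 = 0.0271
- Change score: 1.6/260 + 0.4/43 = 0.0155
- Common slope, (260 × 0.2 + 43 × 0.8)/303 = 0.285: 0.967/260 + 0.625/43 = 0.0183
- Baseline-by-arm: 0.96/260 + 0.36/43 + 0.6²/303 = 0.0133

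The change score is 15% below common-slope ANCOVA (0.0155/0.0183).

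*Case B: SD 0.5 active, 0.3 placebo, 0.3 baseline; ρ = −0.2 active, 0.8 placebo. The arm slopes are −0.333 and 0.8.*

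- Unadjusted: 0.25/260 + 0.09/43 = 0.00305
- Change score: 0.40/260 + 0.036/43 = 0.00238
- Common slope, (260 × −0.333 + 43 × 0.8)/303 = −0.172: 0.2423/260 + 0.1175/43 = 0.00366
- Baseline-by-arm: 0.24/260 + 0.0324/43 + 1.133² × 0.09/303 = 0.00206

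Common-slope ANCOVA is 20% above unadjusted (0.00366/0.00305). The baseline-by-arm model has the lowest variance in both cases.

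**6. Small-sample cost.** These are large-sample formulas. Estimating a slope from about 43 placebo participants adds roughly 1/(43 − 3) = 2.5% to the placebo term, which cancels the gain at ρ = 0.1 but not at 0.3 or 0.5.

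**The case against.** The case for leaving the plan alone is fair in several respects.

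- Allocation is randomised, so the unadjusted contrast is unbiased. No stated figure is wrong and no two sections conflict.
- No decision depends on the contrast. The formal test is single-arm, and dose selection uses a 70% response rate plus safety (protocol 8.5.6).
- Baseline is not ignored. Responder status is an increase from baseline (protocol 6.4.6), and cellular responses are summarised as increases.
- The optional models are labelled exploratory, so the freedom over covariates does not reach the main estimate.
- The gain may be negligible. Prior MERS-CoV or camel exposure and prior MERS vaccine are exclusions (protocol 4.2), so baseline titers could cluster at the assay floor. MERS serology is discretionary, however, and the documents do not report baseline titers.
- A single-slope ANCOVA can lose precision, as case B shows.

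All of this stands, and it limits the point to precision and clarity. The last item changes the form of the model: a baseline-by-arm term deals with both counter-examples. None of it resolves the undefined fold ratio.

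A reader might also infer from protocol 8.5.9 that the sponsor expects antibodies to other coronaviruses to affect the response. The text lists them as a confounder for a model that may be fitted and plans to explore the relationship; it asserts no effect. Nor do the documents say how far T-cell counts vary before vaccination, so no gain for ELISPOT can be claimed from them.

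**Conclusion.** This is a free improvement, not an error. The INO-4700 vs placebo binding antibody contrast should have one stated definition and a pre-specified baseline adjustment.

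The size rests on assumptions the documents do not supply: equal SDs, a common correlation and, for the CI factors, a log10 SD of 0.5 and 43 evaluable placebo participants. On those, variance falls by 1% at ρ = 0.1 (nothing after the small-sample cost), 9% at 0.3 and 25% at 0.5. The gain is near zero if baselines are at the floor.

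Two stronger readings are not supported. One is that the planned comparison is biased or that the primary result is weakened; randomisation and the one-sample test rule that out. The other is that a fold-rise analysis is generally 67% noisier than ANCOVA. That figure holds only at a common correlation of 0.2 with equal SDs, and case A reverses the ordering against a single-slope model.

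The sponsor's memo on discontinuation states that the trial will not proceed to Part 2, so the contrast bears only on the plan as written and on any reuse of its text.

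**What to change.** In SAP 4.3.1, specify the INO-4700 vs placebo titer contrast as an ANCOVA on log10 titer with arm, log10 baseline titer centred at its overall mean, and a baseline-by-arm term, using a robust standard error. Report the adjusted geometric mean ratio with its 95% CI. The baseline-by-arm term is there because allocation is 6:1 and slopes may differ by arm.

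State that the supportive unadjusted ratio is of post-dose geometric means, or of fold-rises if that was intended. Keep the differences in medians as supportive. Antibodies to other coronaviruses can stay in the exploratory regression already planned in SAP 3.6.

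The cost is a sentence or two in the SAP and a short model statement in the program. No extra sample, visit or participant is needed, and the primary test and sample size stay as they are.
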